11.2.2	Minimizing the potential for coercion of patients to participate.....	10
11.3	Potential Risks and Minimization of Risks	10
11.3.1	Risk Associated with Screening and Assessments:.....	10
11.3.2	Risk Associated with Computerized Cognitive Training:	11
11.3.3	Risks Associated with tDCS.....	11
11.4	Potential Benefits and Justification of Risks	12
12.0	Data Handling and Record Keeping	12
13.0	References.....	13

Protocol Summary

Title: Neuromodulation plus cognitive training to improve working memory among individuals with serious mental illness

Abstract:

Background: People with serious mental illness (bipolar disorder and schizophrenia-spectrum illness) often demonstrate impaired neurocognition; in particular, working memory has been proposed as a shared neurocognitive endophenotype of these disorders. Novel non-pharmacological treatments have shown promise, with some evidence that cognitive remediation confers benefit in terms of neurocognitive symptoms and functional performance. The published effect sizes, however, are somewhat modest, prompting researchers to focus on potential “cognitive enhancers” to boost the effects of training. Neuromodulation, specifically transcranial direct current stimulation (tDCS), is one potential enhancing treatment that is considered exceptionally safe and cost-effective.

Study Design: The proposed study aims to investigate the feasibility, acceptability, and initial efficacy of a combined computerized cognitive training and tDCS intervention, using a randomized sham-controlled design including individuals with serious mental illness. This study is a critical first step in advancing the evidence-base regarding treatments that can improve neurocognitive abilities and functional outcome among those affected by psychiatric illness. Examining whether tDCS is a realistic treatment option for individuals with psychiatric illness, and whether adding tDCS to a cognitive training paradigm improves working memory performance beyond the positive effects of training alone, will lay the groundwork for additional investigation with larger samples.

Objectives: 1) determine the feasibility and acceptability of tDCS treatment and computerized cognitive training in this population; 2) examine preliminary efficacy of the combined treatment on main outcome: working memory performance.

Population: Patients aged 18-65 diagnosed with schizophrenia, schizoaffective disorder, or bipolar disorder

Site: University of Michigan

Study Duration: 2 years

Participant Participation Duration: 2 months

Study Design: Randomized controlled trial

Number of participants: 12 completers for Aim 1, 30 completers for Aim 2, 1:1 randomization

Description of Intervention: 2mA stimulation to left dorsolateral prefrontal cortex, 10 treatment sessions; 10 hours of computerized cognitive training

Estimated Time to Complete Enrollment: 2 years

1.0 Background and Significance

Neurocognitive impairment is prevalent among individuals with serious mental illness (SMI; bipolar disorder and schizophrenia-spectrum disorders), and is associated with functional disability beyond the effects of symptoms alone. Although the magnitude of deficits is typically greater amongst people with psychotic illness, the pattern is similar across categorical SMI diagnoses and may represent a dimensional, cross-diagnostic feature of those affected by SMI¹⁻⁴. Among other neurocognitive domains, working memory is commonly impaired in both bipolar disorder and schizophrenia, with some evidence that it represents a shared neurocognitive endophenotype among individuals with SMI^{5,6}. A burgeoning area of research involves neuroplasticity-based treatment called cognitive remediation (also known as cognitive training), defined as “a behavioral training-based intervention that aims to improve cognitive processes (attention, memory, executive function, social cognition or metacognition) with the goal of durability and generalization”⁷. The current evidence generally supports the efficacy of cognitive remediation in mood disorders as well as schizophrenia^{7,8}. However, a broad array of training techniques has been reported in the literature, all of which appear to demonstrate some efficacy but none of which emerge as clearly superior. Therefore, there is a growing emphasis on applying novel techniques in conjunction with remediation paradigms; for example, via a “cognitive enhancer” like transcranial direct current stimulation (tDCS) to boost the effects of cognitive training.

In the context of SMI, tDCS has been identified as a promising treatment to reduce depressive symptoms among individuals with bipolar depression, although not all trials have shown significant benefits^{9,10}. There is also some limited evidence that tDCS may be effective in treating auditory hallucinations and possibly improving cognitive functioning among people with schizophrenia¹¹, although to date most published works were case studies, used single tDCS sessions, or did not include cognitive training concurrent with stimulation. Researchers have concluded that there is potential utility in use of tDCS for cognitive remediation, and have identified the use of tDCS as monotherapy or in combination with cognitive training as an area of future emphasis¹¹.

The proposed study is a critical first step toward a larger RCT, aiming to collect preliminary pilot data on the feasibility, acceptability, and initial efficacy of a combined neuromodulation and cognitive training intervention for individuals with SMI. Thirty participants diagnosed with SMI will be enrolled; participants will be randomized to receive 10 sessions of either active or sham tDCS, and will concurrently complete 10 hours of computerized cognitive training focused specifically on working memory abilities.

2.0 Specific Aims and Study Outcome Measures

2.1 Specific Aims

Specific Aim 1: Determine the feasibility and acceptability of delivering a combined neuromodulation (tDCS) plus cognitive training intervention to outpatients with SMI (n=12). Individuals with SMI, particularly those with neurocognitive impairment, often face barriers to treatment access and retention. The proposed study will incorporate various strategies to support participant retention and promote acceptability, with the hypothesis that participants will be able to tolerate 10, 20-minute sessions of tDCS in the clinic and 10 hours of computerized cognitive training over the course of 4-8 weeks.

****NOTE: Aim 1 corresponds to NCT03338673 registered on clinicaltrials.gov. ****

Specific Aim 2: Collect pilot data on the efficacy of the combined intervention, comparing neurocognitive performance following active tDCS treatment to performance after cognitive training alone (sham tDCS). The proposed analyses will test the hypothesis that active tDCS plus computerized cognitive training will produce a synergistic effect, where performance following the combined treatment will be superior to performance following sham stimulation/cognitive training alone.

****NOTE: Aim 2 is registered on clinicaltrials.gov as NCT05111548****

2.2 Study Outcome Measures

Aim 1: Determine the feasibility and acceptability of delivering a combined neuromodulation (tDCS) plus cognitive training intervention to outpatients with SMI.

Primary outcome: Participant retention, defined as the percentage of enrolled participants who complete the combined intervention.

Secondary outcome: Self-reported treatment satisfaction, as measured on a 1-10 scale at study completion.

Aim 2: Collect pilot data on the efficacy of the combined intervention, comparing neurocognitive performance following combined treatment to performance after cognitive training alone.

Primary outcome: change in working memory performance

Secondary outcome: change in non-working memory comparison measures

3.0 Study Design

3.1 Overview of Experimental Design

Aim 1 (feasibility and acceptability) will include a randomized crossover design, where all 12 participants will receive both the combined intervention (active tDCS plus BrainHQ computerized cognitive training), and computerized cognitive training alone, with starting condition randomly determined. Aim 2 (efficacy) will be a randomized, controlled trial, where half of the participants (n=15) will be randomized to receive active transcranial direct current stimulation (tDCS) plus BrainHQ computerized cognitive training, and half (n=15) will receive sham tDCS plus BrainHQ computerized cognitive training (Table 1). Participants will attend 10 treatment sessions in the clinic. If able to attend daily, participants will complete these sessions in 2 weeks; to allow for unanticipated absences or difficulty with attendance, up to 4 weeks will be permitted for completion. Following completion of these 10 treatment sessions, participants will return after one month of no study contact to complete a follow-up assessment.

3.2 Interventions

Cognitive training: Software licenses for a commercially-available computerized cognitive training package titled BrainHQ will be purchased and provided to each participant (<http://www.brainhq.com/>). To date, more than 30 published manuscripts and abstracts reported on the effects of BrainHQ for individuals with SMI; it also meets each of the 5 criteria recently published by the Institute of Medicine in support of a brain-training program's scientific merit. This program offers a variety of working memory-specific training paradigms, individualized feedback and progress notification, and administrative oversight of training exercises as well as detailed usage reports. BrainHQ can be accessed from any web-enabled computer and has both tablet and mobile applications available on Apple devices.

tDCS: There are data suggesting that tDCS can affect functioning in the prefrontal cortex, an area often implicated in models of neurocognitive dysfunction. In particular, stimulation of the dorsolateral prefrontal cortex (DLPFC) is commonly used; this functional region is believed to underlie executive cognitive functions like working memory and cognitive flexibility, which are popular targets of cognitive training interventions. Because there is no clear guide from the literature on (1) location of electrode placement, (2) frequency of stimulation, or (3) duration of stimulation, the montage and procedures proposed here are guided by the general consensus in the published literature, hypothesized neural circuitry of interest, and what is presumed to be most acceptable to participants. Based on these features, the anticipated montage will include concurrent anodal (excitatory) stimulation of 2 mA over the left dorsolateral prefrontal cortex, and cathodal (inhibitory) stimulation over right dorsolateral prefrontal cortex, over a total of 10 sessions lasting 20 minutes each. Minor deviations are possible but are not expected to significantly increase risk to participants. For example, as new data emerge, we may shift the montage, e.g. cathodal stimulation to parietal region. Participants will complete BrainHQ exercises concurrently during stimulation. All treatment sessions will take place at the Rachel Upjohn Building (RUB).

3.3 Procedures

Participants will include a total of 42 individuals who are self- or clinician-referred in response to advertisements posted in Ambulatory Psychiatry/RUB or in the community. Participants may also be recruited from the Prechter Bipolar Longitudinal Study or [name] & [name]'s studies. Enrollment will occur on a rolling basis, with anticipated enrollment of 1-2 participants per month. Potential participants will

meet with a study coordinator to provide written informed consent; following consent, participants will complete a structured diagnostic interview to confirm eligibility; participants not meeting the inclusion criterion (below) will be compensated for their time and excluded from further participation. To minimize attrition and missing data, participants will be compensated for each visit (up to \$200 total); study staff will also provide reminder phone calls for appointments, and may arrange transportation via cab if and when possible.

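### The same 12, 30 and 42 serve both as people enrolled and as completers, with no attrition allowance, and 42 fit one two-year study only in the upper part of the stated recruitment range

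*Combined protocol and SAP*

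**What the plan says.** **Size as completers.** The Protocol Summary gives "12 completers for Aim 1, 30 completers for Aim 2, 1:1 randomization".

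**Size as people entered.** Section 3.3 says "Participants will include a total of 42 individuals". Section 1.0 says "Thirty participants diagnosed with SMI will be enrolled". Section 3.1 randomises 15 to active and 15 to sham stimulation in Aim 2 and has 12 participants in Aim 1. The schematic in Section 3.4 shows the same group sizes.

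**Rate and time.** Section 3.3 describes rolling entry "with anticipated enrollment of 1-2 participants per month". The Protocol Summary lists "Study Duration: 2 years", "Estimated Time to Complete Enrollment: 2 years" and "Participant Participation Duration: 2 months".

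**Losses.** No attrition rate, replacement rule or split of accrual between the aims is stated. Section 2.1 acknowledges that this population meets obstacles to staying in treatment, and Section 2.2 makes retention the Aim 1 primary outcome. Sections 4.4.2 and 5.2.3 provide for withdrawal, and Section 3.3 provides for exclusion after consent.

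**The concern.** A completer target and an enrolment target can share one number only if nobody is lost. The plan foresees losses in several places but carries none of them into its numbers, so a reader cannot tell whether 30 is the number to be randomised or the number expected to finish.

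The two time statements raise a related difficulty. Enrolment is given the full length of the study, yet the last person to enter still needs two months. Either entry ends at about month 22 or the study runs past two years. The stated rate leaves little room for this if both aims share the period.

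At stake is whether the stated size and timeline can be relied on when the trial is run and reported. If the completer count falls below 30, the documents do not say whether the target has been missed or was never meant in that sense.

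**Working it through.** **Inputs from the documents.** 12 and 30 completers, 24 months of study, 24 months of enrolment and 2 months per participant (Protocol Summary); 42 people in total and 1 to 2 per month (Section 3.3); 15 + 15 in Aim 2 (Section 3.1).

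**Assumptions.** The loss rate is not in the documents; 10-20% is used for illustration. People who fail screening after consent are not counted in the 42; if they are, the position is worse.

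**1. Reproduce the stated total.** 12 + 30 = 42. The 42 people in Section 3.3 are therefore exactly the sum of the two completer targets, with nothing added.

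**2. Completers from the stated enrolment.** Completers = enrolled × (1 − loss). For Aim 2:
- 0% loss: 30
- 10% loss: 30 × 0.90 = 27
- 20% loss: 30 × 0.80 = 24

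**3. Enrolment needed if completers are meant.** Needed = target / (1 − loss), rounded up within each aim:
- 10% loss: 12/0.90 gives 14 and 30/0.90 gives 34, in total 48
- 20% loss: 12/0.80 = 15 and 30/0.80 gives 38, in total 53

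**4. Entries in two years at the stated rate.** Entries = rate × entry months. The 22-month column lets the last entrant finish within 24 months (24 − 2 = 22).

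| Rate per month | 22 entry months | 24 entry months |
|---|---|---|
| 1 | 22 | 24 |
| 1.5 | 33 | 36 |
| 2 | 44 | 48 |

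**5. Rate needed for 42 entries, with no loss.** 42/24 = 1.75 per month; 42/22 = 1.91 per month.

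**6. Loss that the top rate can absorb and still give 42 completers.** This goes beyond the stated 42 recruits. Over 22 months: 1 − 42/44 = 4.5%. Over 24 months: 1 − 42/48 = 12.5%, but the last entrants then finish after two years.

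**7. What the midpoint rate leaves for Aim 2.** If both aims share the period and Aim 1 fills first: 33 − 12 = 21 or 36 − 12 = 24, before any loss.

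**8. Alternative reading: two years for Aim 2 alone.** 30/22 = 1.36 per month, below the midpoint of 1.5.

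**9. Duration implied by the rate for 42 enrolled.** Duration = 42/rate + 2:
- 2 per month: 21 + 2 = 23 months
- 1.5 per month: 28 + 2 = 30 months
- 1 per month: 42 + 2 = 44 months

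**10. Chance variation.** If entries follow a Poisson process (an assumption), the probability of at least 42 by month 22 is 64% at 2 per month and 7% at 1.5 per month.

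**The case against.** The best defence concerns accrual, and much of it stands.

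- **The range covers the target.** At 2 per month, 44 to 48 people enter in 22 to 24 months, so the stated rate does not rule out 42.
- **Two years is not a hard limit.** The enrolment time is labelled an estimate and the rate is described as anticipated. Section 4.4.4 gives examples of reasons to end the study early, and none is a calendar date.
- **The aims may not share the period.** Each has its own registration (notes in Sections 2.1 and 2.2), and Section 1.0 describes a study of thirty. If the two years belong to Aim 2, its 30 are within reach below the midpoint rate. Against this, the Protocol Summary gives one duration beside both aims' numbers, and Section 3.3 applies one rate to all 42. The shared reading is the plainer one, but it is not certain.
- **Completers are not the number analysed.** Section 6.2 keeps participants who miss sessions or training hours and uses their outcome data. Section 5.2.4 seeks the final assessments from those who stop early. The Aim 2 comparison can therefore include more people than complete treatment.
- **Aim 1 does not presuppose poor retention.** It measures retention, and Section 2.1 hypothesises that participants will tolerate the course.

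A reader might infer from the midpoint figures that Aim 2 will probably end well below 30, or that its comparison will be undersized or unbalanced. The documents do not support this. It would need a closing date at two years, one shared period and Aim 1 filled first, none of which is stated. Nor does the plan give a power, effect size or precision target against which to call the comparison undersized.

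None of this reconciles the completer counts with the enrolment counts.

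**Conclusion.** The point holds in two parts of unequal strength.

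**Size.** The plan is inconsistent as written, and this needs no assumption. The Protocol Summary counts completers, while Sections 1.0, 3.1 and 3.3 count the same people as enrolled or randomised. The two agree only with zero attrition. How far completers fall below 30 depends on a loss rate that the documents do not give; the 24 to 27 rests on the assumed 10-20%.

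**Time.** Two years for enrolment and two years for the whole study cannot both hold exactly when each participant takes two months, unless entry ends early. If one period covers both aims, 42 enrolled requires the upper part of the stated range. The 21 to 24 left for Aim 2 at the midpoint is conditional on that reading, on Aim 1 filling first and on recruitment closing with the period. It is not a forecast that Aim 2 will fall short. Nor can it be concluded that recruitment must continue past 24 months, since that is a resourcing decision on which the documents are silent.

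**What to change.** Reconcile the Protocol Summary with Sections 1.0, 3.1 and 3.3 in one of two ways:

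1. State 12 and 30 throughout as participants enrolled or randomised, and add an expected completer range under a stated retention assumption (for example 24 to 27 of 30 at an assumed 10-20% loss).
2. If completers are intended, keep 12 and 30 as completers and restate the enrolment total (at an assumed 10-20% loss, 14 to 15 for Aim 1 and 34 to 38 for Aim 2, in total 48 to 53), with a replacement rule if one is to be used.

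The documents do not show which is meant, so the choice is the sponsor's.

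In the Protocol Summary, restate the study duration so that it includes the two months after the last entry and matches the stated rate. For 42 enrolled this is about 23 to 44 months, or about 30 at 1.5 per month; the second option lengthens it. Say whether the period covers both aims or Aim 2 alone.

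The cost is a less favourable stated timeline or completer count. Under the first option the number recruited does not change; under the second it rises.

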3.4 Schematic

Aim 1.

	Week 0	Weeks 1-4	End of Week 4	Weeks 5-8	Week 8
Group A (6 participants)	Baseline assessment	tDCS + BrainHQ	Mid-point assessment	BrainHQ	Post-treatment assessment
Group B (6 participants)		BrainHQ		tDCS + BrainHQ	

Aim 2.

	Week 0	Weeks 1-4	End of Week 4	Weeks 5-8	Week 8
Group A (15 participants)	Baseline assessment	Active tDCS + BrainHQ	Post-treatment assessment	No contact	Follow-up assessment
Group B (15 participants)		Sham tDCS + BrainHQ			

4.0 Study Participants

4.1 Inclusion Criteria

(1) age 18-65, (2) diagnosis of bipolar disorder I or II, schizoaffective disorder, or schizophrenia, as confirmed by structured diagnostic interview, and (3) willingness to complete computerized cognitive training and undergo brain stimulation procedures.

4.2 Exclusion Criteria

(1) history of neurological illness or brain injury (e.g., stroke), (2) history of loss of consciousness > 20 minutes, (3) diagnosed intellectual disability, (4) current (i.e., past 30 days) substance use disorder, (5) current mania (YMRS \geq 10) or moderate depression (HAM-D \geq 17) or severe psychosis (PANSS positive symptom total \geq 35), (6) serious suicidal ideation/behavior (endorse questions 4 or 5 or suicide behaviors within the past 3 months, according to the C-SSRS), (7) pregnant or trying to become pregnant, or currently lactating, (8) presence of metal (except titanium) or electrical implants in the brain or skull (e.g., surgical clips, deep brain stimulator, cochlear implants, splinters/fragments, skull plate), (9) presence of implanted medical devices elsewhere in the body (e.g., cardiac pacemaker or medical pump).

4.3 Strategies for Recruitment and Retention

Recruitment will be from the outpatient psychiatry programs at the University of Michigan Health System, from flyer advertisements, and by clinician referral. The recruitment process is designed to limit interference with clinical care and assure the informed participation of patient participants. By obtaining a waiver of consent for screening purposes, recruitment is facilitated by pre-review of computer-based medical records to identify potential research participants who have contacted the Department of Psychiatry. In addition, we will scan umhealthresearch.org, the UM registry of individuals who are interested in participating in health research. Study coordinators will make contact with clinic staff to interview patients who express an interest in a study, or who appear eligible based on initial review of electronic records. For all patients who are screened for the study, we will contact their clinician, if not already done during pre-screening (psychiatrist and/or psychotherapist), notify them of their patient's interest and verify that the participant is eligible to participate. The patient's clinician(s) will also be notified via a memo when the patient has enrolled and is scheduled for the study treatment.

4.4 Treatment Assignment Procedures

4.4.1 Randomization Procedures

Following baseline assessment, participants will be randomized to complete either the combined treatment (active tDCS plus cognitive training) or cognitive training alone (sham tDCS). Participants and clinical assessors will be blinded to condition; at the post-treatment assessment visit, participants and the assessor will guess group assignment to evaluate how well the blind was maintained.

4.4.2 Reasons for Withdrawal

During the pre-screening process, participants who are found to be non-eligible, before formal signing of a consent form, will be considered *not enrolled*, and all data related to that participant will be destroyed. Participants who consent, and are found not eligible during the assessment and screening will be considered *screen failures*, and all research and identifying data will be destroyed, except for the consent form and limited information to document the screen failure (age, gender, diagnosis, specific reason for exclusion). Participants who leave the study after signing the informed consent, and after being deemed eligible/enrolled/randomized, will be considered *withdrawn*. Participants may withdraw from the study at any time and for any reason. Participants may be withdrawn by the investigator when continued participation would present an unacceptable risk to the participant. This would include, but is not limited to, significant adverse events related to the device, (e. g., intolerable discomfort), or participants who experience severe symptom worsening, including suicidal thoughts or behaviors, which require hospitalization.

